#### **4.3.4 Procedures for Subject Follow-up**

Every effort should be made to educate the subjects on the importance of remaining in the study and attending scheduled study visits up to the end of clinical study, including those required after early discontinuation of investigational product.

All subjects who either complete the Active Treatment Period or who prematurely discontinue investigational product are required to undergo the Visit 6 / Early Termination (Day 29 clinical assessments according to the [Schedule of Assessments](#)).

If a subject prematurely discontinues investigational product and is unwilling or unable to attend visits during the Active Treatment Period in-person according to the visit schedule, he / she will be contacted by telephone or other methods to assess study outcomes and vital status. The only exception to this requisite is for subjects who withdraw consent for any form of contact ([Section 4.3.3](#)).

Refer to [Section 10.3.6](#) for early study termination rules for futility and efficacy based on the 3 planned interim analyses, respectively. If the study is terminated early for futility, subjects still in the Active Treatment Period should not receive further investigational product and should return to the site for the Early Termination Visit (Visit 6 [Day 29]); subjects in the Follow-up Period should return for their EOS Visit as defined in [Section 3.6](#). If the study is terminated early for efficacy, enrollment will cease upon the announcement of the decision to stop the study.

Other subject follow-up options to collect MACE endpoints and vital status should be pursued according to local laws and regulations. If 1 of these alternate methods to collect

MACE endpoints and vital status is acceptable to the subject, then the subject will be deemed not to have withdrawn consent for follow-up.

Study completion is defined in [Section 3.6](#).

#### **4.3.5 Subjects Potentially Lost to Follow-up**

Investigators should make every effort to contact subjects who are potentially lost to follow-up, including pursuing any alternative contact methods permitted by local regulations or agreed upon by the subject. As permitted by local regulations, a third party may be used to locate alternative subject contact information in the public domain that will be provided to the investigator. The following procedures should be performed before a subject will be deemed lost to follow-up at the end of the study:

1. At least 3 documented subject contact attempts should be made (eg, in-person visit, phone, mail, email).
2. If the subject cannot be directly contacted, utilize all contact information provided when the subject signed consent (next of kin, “referring (non-study) physician”, etc.).
3. If all contact attempts are unsuccessful, available sources such as electronic medical records and death registries should be reviewed on an ongoing basis until EOS to attempt to locate the subject, as permitted according to local and national laws.
4. A patient locator service should be utilized (as allowed by local laws).
5. These subject contact procedures should be followed by the sites, who will be encouraged to continue their attempts to locate the subject or next of kin up until the database lock before designating a subject lost to follow-up.

#### **4.3.6 Replacement Policy**

Subjects withdrawn from the study will not be replaced.

### **5 Study Interventions**

#### **5.1 Description of Investigational Product(s)**

##### **5.1.1 CSL112**

The study product, CSL112, will be manufactured by CSLB in accordance with Good Manufacturing Practice (GMP) guidelines and local regulatory requirements.

**Apolipoprotein A-I**

---

The active component of CSL112 is apoA-I, which is purified from human plasma. Apolipoprotein A-I is formulated with PC and stabilized with sucrose and cholate as excipients. CSL112 will be provided to the site as a sterile, slightly yellow, lyophilized powder containing 2 g total protein in a 100-mL glass bottle with a rubber stopper and an aluminum cap. Before use, each bottle of CSL112 is reconstituted with 50 mL of water for injection, yielding approximately 57 mL of ready-for-use product. For the 6 g CSL112 dose to be used in this study, 3 bottles will be reconstituted for an approximate total of 170 mL of product. Once reconstituted, CSL112 is a pale yellow solution with foaming characteristics.

Further details regarding preparation of CSL112 are specified in the Investigator Brochure and site investigational medicinal product manual (ie, Site IMP Manual).

**5.1.2 Placebo**

The placebo product will be manufactured by CSLB in accordance with Good Manufacturing Practice guidelines and local regulatory requirements.

The placebo product will be **CCI** in water (**CCI**) for IV infusion. An equivalent amount of placebo (approximately 170 mL) to CSL112 will be intravenously infused in a vein (peripheral or central) over 2 hours. Placebo product will be provided to the site as 50 mL vial of a registered 25% albumin solution. The placebo solution will comprise **CCI** **CCI** to yield a 4.4% albumin solution. Further details regarding the preparation of the placebo are specified in the Site IMP Manual.

**5.2 Packaging, Labeling, Supply and Storage**

**5.2.1 Packaging and Labeling**

CSL112 and placebo product will be packaged and labeled according to current ICH GMP and GCP guidelines, and national legal requirements.

Commercially-available, sterile, water for injection and **CCI** will be purchased by the study sites for use in the preparation of CSL112 and placebo, respectively.

**5.2.2 Supply and Storage**

CSL112 and placebo will be supplied to the study sites by CSLB or delegates.

CSL112 must be stored under temperature-monitored conditions (+2°C to +30°C, inclusive) in a secure storage area.

**Apolipoprotein A-I**

---

Placebo (albumin) must be stored under temperature-monitored conditions (+2 to +8°C, inclusive) in a secured storage area.

CSL112 and placebo **MUST NOT BE FROZEN**, as this may disrupt the protein structure of each product.

CSL112 and placebo must be protected from light during storage. The individual packaging holding the CSL112 and placebo bottles is sufficient for light protection.

Further details regarding specific storage conditions of CSL112 and placebo are specified in the Site IMP Manual.

**5.3            Accountability and Destruction**

All supplies of investigational product(s) must be accounted for throughout the study. Records for the delivery of investigational product to the study site, the inventory at the study site, the use by each subject, and the destruction or return of investigational product to CSLB must be maintained by the investigator (or delegate). The records will include dates, quantities, and unique code numbers assigned to investigational product and unique code numbers assigned to the subjects.

Information on the destruction of CSL112 or placebo is provided in the Site IMP Manual.

**5.4            Other Intervention(s)**

Not applicable.

**5.5            Dose Modification**

Not applicable.

**6               Allocation, Dosing and Administration**

**6.1            Allocation to Treatment**

**6.1.1        Subject Assignment**

After providing written informed consent, the subject will be issued a study-level unique subject identification number via an interactive response technology (IRT) system. The subject identification number will be used to identify the subject for the duration of the study. Subject identification numbers will not be reassigned or reused.

### **6.1.2 Randomization Procedures**

Eligible subjects will be randomized in a 1:1 ratio to receive CSL112 or placebo by means of the IRT. A centralized randomization schedule will be used. The randomization schedule will be stratified by subject's index MI type (STEMI vs NSTEMI), whether they are managed with PCI or medically managed for the index MI, and region (North America, Latin America, Western Europe, Central and Eastern Europe, or Asia Pacific). A balanced distribution of STEMI and NSTEMI is desired, and may require implementation of a limit on an index MI type during the conduct of the study. To ensure the study blind is maintained, the IRT external service provider will prepare the study randomization code according to the specifications provided by the CSLB statistician. The external service provider will keep the randomization code on file.

### **6.1.3 Blinding Procedures**

#### **6.1.3.1 Blinding Method**

This study is a double-blind study and, therefore the reference placebo product matches the physical characteristics of the investigational product after preparation. Once prepared according to the instructions given in the Site IMP Manual and transferred to IV infusion bags, CSL112 and placebo match in color and foaming characteristics.

Investigational site staff, including the investigator, will be blinded to treatment allocation. Subjects and CSLB staff participating in the conduct of the study will also be blinded to treatment allocation (double-blind). Study site personnel delegated by the investigator will administer the investigational product by IV infusion in a suitable peripheral or central vein.

Unblinded study site personnel delegated by the investigator will prepare the investigational product and the IV infusion bag and infusion set for administration. The unblinded study site personnel will also ensure the contents remain blinded to the subject and the blinded study site personnel who will be conducting safety assessments. Unblinded study site personnel are not to administer the investigational product and will not be involved in conducting or recording any study assessment procedures (ie, in the care of the subject).

Adequate procedures will be in place to ensure the integrity of the blinded data within CSLB and the study sites. **The investigator and other blinded study staff must not review the results of a lipid panel test (specifically the HDL cholesterol level) during the Active Treatment Period as the results may unblind treatment assignment.**

### **6.1.3.2                   Breaking the Blind for an Emergency**

The randomization code for individual subjects may be unblinded to a site during the study in emergency situations for reasons of subject safety, if knowing treatment assignment will change subject management. In case of an emergency situation for the reason of subject safety, the investigator should use IRT to identify the treatment allocation for a subject. Whenever possible, the investigator should consult with the study hotline before unblinding the randomization code. The reason for unblinding the randomization code must be fully recorded in the subject's source documents, and the investigator must follow the defined procedures provided in the study reference manuals. The subject's treatment allocation should not be recorded in the subject's source document.

### **6.1.3.3                   Planned Unblinding Procedures**

Three unblinded interim analyses and periodic unblinded safety reviews are planned for this study for the purposes of safety monitoring activities and efficacy assessment by the IDMC ([Section 10.3.6](#)). With authorization by CSLB, the IRT external service provider will provide the randomization code to the unblinded statistician (external service provider) performing analyses for the IDMC. At the end of the study, CSLB will authorize that the study be unblinded after database lock. The randomization codes will be provided to the study statistician / delegate.

CSLB Global Clinical Safety and Pharmacovigilance personnel may unblind the randomization code from the IRT to facilitate assessment of suspected unexpected serious adverse reactions (SUSAR) experienced by any subject for expedited reporting to regulatory authorities. MACE are exempt from suspected unexpected serious adverse reactions reporting (see [Section 9.6.4](#)).

## **6.2                       Dosing and Administration**

The investigator (or delegate) will administer the investigational product only to subjects who provide written consent, meet the inclusion criteria and none of the exclusion criteria ([Section 4.1](#)) and have confirmed infusion eligibility ([Section 4.2](#)), and will follow the administration parameters outlined in [Table 1](#) as well as the procedures described below. Infusion 1 must be administered in the timeframe as detailed in [Section 4.2.1](#). Infusions 2, 3, and 4 may be administered in the hospital or an outpatient setting at least 5 days apart (see [Schedule of Assessments](#)).

**Table 1** **Investigational Product Dosing Characteristics**

Administration parameter	CSL112 6 g	Placebo
Route	Intravenous	Intravenous
Anatomical location	Vein (peripheral or central)	Vein (peripheral or central)
Infusion rate	approximately 170 mL over 2 hours	approximately 170 mL over 2 hours

The blinding procedures are described in [Section 6.1.3](#). After preparation, CSL112 and placebo will be identical in physical appearance at administration. Administration of the investigational product should be completed within 6 hours of preparation of the solution. A dedicated IV line should be used for administration of investigational product. Patency of the IV line should be ensured before the start of the infusion. Subjects should be advised to sit down or lie in a semi-supine position while receiving the infusion. Subjects randomized to the placebo group will receive a volume of placebo matched to the corresponding CSL112 infusion volume.

**After completion of the infusion, the IV line should be flushed with saline. The end of the saline flush defines the end of infusion.**

Study site personnel who are medically qualified to recognize and treat drug hypersensitivity reactions must be available together with medications and equipment to treat such reactions. All possible drug hypersensitivity reactions require follow-up until resolution ([Section 9.1.2.1](#)).

## **6.3 Treatment Compliance**

All doses of investigational product will be administered by IV infusion. Each subject will be considered to have received a complete dose of investigational product if they receive at least 80% of investigational product per infusion.

## **7 Contraindications, Permitted Therapies and Prohibited Therapies**

### **7.1 Contraindications and Precautions to Further Dosing**

CSL112 has previously been administered to humans. Potential risks and guidance to the investigator for use of CSL112 are provided in the current version of the Investigator's Brochure. The administration of CSL112 to any subject not meeting the eligibility criteria for this study, or to any subject not enrolled in this study, is prohibited.

### **Apolipoprotein A-I**

---

There is potential for allergic reactions or hypersensitivity to CSL112 in certain individuals, given the constituents of the product. CSL112 consists of apoA-I purified from human plasma that may contain IgA and PC derived from soy beans. Therefore, investigators should ensure that subjects do not have a positive history of IgA deficiency or antibodies to IgA and that the subjects are not allergic to either soy bean or peanuts (there is a documented risk of cross reactions to soy in known peanut allergy sufferers).

Regarding placebo, the albumin prescribing information contains warnings for allergic and anaphylactic like reactions and notes hypersensitivity reactions under adverse reactions. The reported rate of anaphylaxis cases is very low. In addition, there has been no correlation between increasing strength and anaphylactic reaction. Due to limited data available for dosage, no trend of the association between dose and anaphylactic reaction can be made.

In the event that a subject experiences signs or symptoms of a hypersensitivity reaction requiring hospitalization or urgent intervention, or there is suspected angioedema during infusion of investigational product, the current infusion and all subsequent infusions must be immediately discontinued. The subject must receive immediate medical assessment and indicated supportive management per the institutional standard of care ([Section 9.1.2.1](#)).

If a subject experiences a serious adverse event (SAE) of hypersensitivity reaction within 72 h of administration of a dose of investigational product, or there is suspected angioedema during infusion of investigational product, additional doses of investigational product should not be administered.

## **7.2 Permitted Therapies**

Concomitant medication typical of those taken by the intended target population (ie, ACS-related treatments) is permitted throughout the study unless prohibited as described in [Section 7.3](#) and must be recorded as outlined in [Section 8.1.1.3](#).

### **7.2.1 Evidence-based Medical Therapy**

All randomized subjects should receive evidence-based post-MI care according to local standards of care and national practice guidelines (without a local standard, the current guideline from the American College of Cardiology / American Heart Association / European Society of Cardiology [ACC / AHA / ESC] etc. should be utilized). Close adherence to professional society evidence-based medical therapy in ACS will be emphasized during study conduct, including use of appropriate revascularization (PCI) and pharmacological treatments, such as dual anti-platelet therapy (ie, aspirin in combination with a P2Y12

inhibitor, or aspirin in combination with another anti-platelet agent), angiotensin-converting enzyme (ACE) inhibitors (or angiotensin II receptor blockers [ARBs] for patients intolerant to ACE inhibitors), beta-blockers, statin and other lipid lowering medications.

All concomitant treatment for ACS including the dose, route of administration, and frequency must be documented in the eCRF, including variance from evidence-based medical therapy (eg, aspirin, adenosine diphosphate receptor inhibitors, and statins) ([Section 8.1.1.3](#)).

### **7.3 Prohibited Therapies**

The following therapies are NOT PERMITTED during the study:

- Treatment with anticancer therapy (chemotherapy, immunotherapy, radiotherapy, targeted therapy, or gene therapy) at any time during the study.

NOTE: Use of low dose chemotherapy for treatment of a condition other than cancer (eg, rheumatic disease) is permissible (see [Section 4.1.2](#)).

- Administration of any other investigational agent within 3 months before the first administration of investigational product or at any time before the subject's completion of the study.

Subjects are not to be enrolled into the study if they received any prohibited therapy within 3 months of screening. If administration of any prohibited therapy becomes necessary during the study for medical reasons, the subject may be discontinued from receiving further infusions of investigational product. The requirements for handling early discontinuations from investigational product are described in [Section 4.3.1](#).

### **7.4 Lifestyle Restrictions**

There are no study-specific dietary or lifestyle restrictions for subjects who participate in the study.

All randomized subjects should receive evidence-based post-MI care according to local standards of care and national practice guidelines (without a local standard, the current guideline from the ACC / AHA / ESC etc. should be utilized). Close adherence to these guidelines for ACS regarding diet and lifestyle restrictions, physical activity and / or cardiac rehabilitation, and tobacco smoking cessation is to be emphasized during study conduct as per site's standard practice and will be assessed at Days 90, 180 and 365.

## **7.5        Overdose**

For this study, overdose is defined as any single dose 50% greater than the total volume of investigational product ([Section 5.1.1](#)) or an infusion rate that exceeds 3 mg/kg/min of sucrose. The effects of any potential overdose with CSL112 have not been studied, and therefore infusion rate for the investigational product should be maintained as per [Table 1](#) ([Section 6.2](#)). Total duration of the infusion should not be less than 1 hour. Any suspected overdose resulting in an AE that is considered by the investigator to be medically significant must be reported as a SAE (see [Section 9.6.3](#)). See [Section 9.6.6](#) for overdose reporting requirements.

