8.2.4 Durations

Durations of events (eg, duration of an AE or medication) calculated in days will use only dates based on the algorithm given below:

- (End date – Start date) + 1

Durations calculated in hours (h), such as duration of infusion, will be calculated using date/time variables shown below:

- (End date/time – Start date/time)

Where durations calculated in days have to be reported in months or years, the following approach will be taken:

$$\text{Months} = \text{days} / 30.4375$$

$$\text{Years} = \text{days} / 365.25$$

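### The 1-hour minimum infusion time does not by itself keep a full CSL112 dose within the protocol's own sucrose limit at about 50 to 55 kg

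*Protocol*

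**What the plan says.** Protocol Section 7.5 contains three rules that bear on infusion speed.

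- Overdose includes "an infusion rate that exceeds 3 mg/kg/min of sucrose". The other limb of the definition concerns excess volume.
- Because overdose effects have not been studied, the "infusion rate for the investigational product should be maintained as per" Table 1. Table 1 (Section 6.2) gives "approximately 170 mL over 2 hours".
- "Total duration of the infusion should not be less than 1 hour".

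Other places fix the terms:

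- Section 6.2, on timing: "The end of the saline flush defines the end of infusion".
- Section 5.1.1: three bottles are used per dose, each "yielding approximately 57 mL of ready-for-use product", so about 171 mL.
- Section 4.1.2, exclusion criterion 5: subjects under 50 kg are not enrolled.
- Section 1.4: 6 g over 2 hours (50 mg/min) is described as the maximum rate, and the resulting sucrose rate at 50 kg is put below 1.7 mg/kg/min.
- Section 6.3: a dose counts as complete for subjects "if they receive at least 80% of investigational product per infusion".
- SAP 8.2.4: "Durations calculated in hours (h), such as duration of infusion, will be calculated using date/time variables shown below", that is, end minus start.
- SAP 11.1: the sucrose content (9900 mg) and the formula used to count overdoses by rate.

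**The concern.** The 1-hour sentence matters only when an infusion has already run faster than Table 1 instructs. It is then the only numeric minimum on duration that the protocol gives. If a full dose can satisfy that minimum and still meet the same section's overdose definition, the minimum is set too low for the lightest eligible subjects.

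What is at stake is internal consistency of a safety rule, not the efficacy analysis. Section 1.4 names acute kidney injury as the concern with intravenous sucrose. The trial admits subjects with eGFR down to 30 mL/min/1.73 m² and allows dosing from 12 hours after contrast.

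**Working it through.** **Inputs.** Sucrose per full dose 9900 mg and reference volume 170 mL (SAP 11.1); limit 3 mg/kg/min and minimum 60 min (Protocol 7.5); lowest eligible weight 50 kg (Protocol 4.1.2); instructed time 120 min (Table 1).

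**Formula (SAP 11.1).** Rate = (volume / 170) × 9900 / (minutes × kg).

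**1. Reproduce the plan's own figure.** 170 mL, 120 min, 50 kg: 9900 / (120 × 50) = 1.65 mg/kg/min. This agrees with the value below 1.7 in Section 1.4.

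**2. Full dose at the 1-hour minimum.** The last column is the time at which the limit is just met, 9900 / (3 × kg).

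| Weight (kg) | Rate at 60 min (mg/kg/min) | Minutes needed for 3.00 |
|---|---|---|
| 50 | 9900 / 3000 = 3.30 | 66.0 |
| 52 | 3.17 | 63.5 |
| 54 | 3.06 | 61.1 |
| 55 | 3.00 (limit not exceeded) | 60.0 |

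Break-even weight: 9900 / (3 × 60) = 55.0 kg. For 171 mL the formula gives 3.32 at 50 kg, with break-even at (171/170) × 9900 / 180 = 55.3 kg. So the excess is about 10% (10.0% or 10.6%) and the upper weight is about 55 kg. If 9.9 g is a rounding of 9.85 to 9.95 g, the rate at 50 kg is 3.28 to 3.32 and the break-even weight 54.7 to 55.3 kg.

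**3. Volume needed.** At 50 kg and 60 min the limit is passed only above 3 × 50 × 60 / 9900 × 170 = 154.5 mL, or 90.9% of 170 mL. An 80% dose gives 0.8 × 9900 / 3000 = 2.64.

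**4. Effect of the flush.** The flush falls inside the recorded infusion time, so product runs in less than that time. The documents do not give its length. Assuming 1, 5 or 10 minutes within a 60-minute total, the product rate at 50 kg is 9900 / (59 × 50) = 3.36, 9900 / (55 × 50) = 3.60 or 9900 / (50 × 50) = 3.96. Break-even weights are 55.9, 60.0 and 66.0 kg.

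**5. Check of a flow cap of 145 mL/h.** Sucrose delivered: (145 / 60) × (9900 / 170) = 140.7 mg/min.

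- At 50 kg: 140.7 / 50 = 2.81 mg/kg/min.
- Time for 170 mL: 170 / 145 × 60 = 70.3 min; for 171 mL, 70.8 min.
- Weight at which the cap would just meet the limit: 140.7 / 3 = 46.9 kg, which leaves room for some weight loss after screening.
- Flow that would just meet the limit at 50 kg: 3 × 50 × 60 / (9900 / 170) = 154.5 mL/h, so 145 has a small margin.
- Table 1 flow, for comparison: 170 / 2 = 85 mL/h.

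**The case against.** The strongest reply is that Section 7.5 already covers the case. The sucrose limit is itself weight-based, the Table 1 rate is to be maintained, and the 1-hour sentence is a further condition rather than leave to infuse in an hour. A 60-minute full dose at 50 kg departs from Table 1, meets the overdose definition, has to be recorded under Section 9.6.6 and is counted under SAP 11.1. No text says that the 1-hour figure was derived from the sucrose limit. All of this stands, and it is why the point is minor. It does not remove the mismatch: the only numeric floor on duration still lets through what the same section calls an overdose.

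A reader might infer more: that the protocol endorses 1-hour infusions in light subjects, or that subjects are being exposed to harmful sucrose rates. The documents do not support either reading. The instruction is 2 hours, no frequency of fast infusions is given, and nothing shows harm at 3.0 to 3.3 mg/kg/min.

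Three further objections limit what can be claimed.

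- A cap of 145 mL/h is still 145 / 85 = 1.7 times the Table 1 flow, so it does not bring the backstop down to the maximum described in Section 1.4. Its purpose is only to hold the 3 mg/kg/min limit.
- The documents describe no separate end-of-product time, so adherence to a product-only limit would rest on the pump setting and could not be verified from the recorded duration.
- Preparation detail is left to the Site IMP Manual and procedural detail to study manuals that are not available here. Whether these already set a pump rate cannot be determined.

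**Conclusion.** The point holds as a minor, cheap improvement. Taken alone, the 1-hour minimum allows a full CSL112 dose to exceed the section's sucrose limit at about 50 to 55 kg, by about 10% at 50 kg. The exposed window at 50 kg is 60 to 66 minutes. Counting a flush within the hour raises both the excess and the weight range, by an amount that depends on an undocumented flush length.

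The conclusion rests on a steady flow, near-full volume (above 154.5 mL at 50 kg and 60 minutes), the 9900 mg content in SAP 11.1, and a departure from the 2-hour instruction. It concerns CSL112 only, because the sucrose figure is for the active product. It has no bearing on endpoints, power or the efficacy analysis.

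**What to change.** In Section 7.5 keep the 1-hour sentence for all infusions and add to it: *and product, excluding the saline flush, should not be delivered faster than 145 mL/h.*

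A flow cap is preferable to a longer minimum written for full-volume infusions only. Replacing the present sentence with such a minimum would leave partial doses without any floor. For example, an 80% dose over 40 minutes at 50 kg gives 0.8 × 9900 / (40 × 50) = 3.96 mg/kg/min, whereas today's 1-hour rule holds that dose to 2.64 on recorded time. A cap on flow covers partial volumes and interrupted infusions as well, and the flush cannot dilute it.

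Leave the Table 1 2-hour rate, Section 1.4 and SAP 11.1 unchanged.

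Cost: one added clause and a slightly stricter limit for sites. Because the change touches subject safety and study conduct, Section 13.3 puts it in a protocol amendment with IRB/IEC approval, not only a site notice. It can be bundled with the next amendment. Sample size and SAP programming are not affected.
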